9.3.13 Post-surgical ophthalmological adverse events

Patients who develop post-surgical complications such as ocular inflammation and raised IOP should be treated according to local standard of care procedures.

Intraocular inflammation worsening during the course of treatment with the protocol defined anti-inflammatory regimen (see [Section 9.2.2](#) Intraocular Injection) or persisting or occurring after the completion of the protocol defined anti-inflammatory regimen must be recorded as a post-surgical ophthalmological adverse event.

In this setting the treatment and follow-up of the patient will be at the discretion of the investigator, guided by the severity and longevity of the inflammation, in an effort to minimize the risk of loss of visual function as a result of the ongoing inflammatory process. In the situation where the intraocular inflammation is clinically worsening the presence of an intraocular infection should be excluded.

Treatment with high dose, oral corticosteroids (1 mg/kg/day for patients ≥ 50 kg; 0.5 mg/kg/day for patients < 50 kg; maximum dose not to exceed 80 mg/day for children < 16 years) is recommended for any patient manifesting worsening intraocular inflammation (eg, $\geq 2+$ for anterior chamber cells, ≥ 2 vitreous haze and/or cells, the presence of vitreous snowballs or retinal vasculitis). In such cases, the oral corticosteroids should be continued until the ocular inflammation is resolved and then tapered as appropriate.

Raised IOP greater than 30 mmHg must be recorded as a post-surgical adverse event and may be treated with IOP lowering drops with the patient reviewed within a week. If the IOP remains greater than 25 mmHg another pressure lowering drop will be added and the patient reviewed again within a week. This sequence will be repeated until the IOP remains below 25 mmHg. For increases in IOP occurring while the patient is receiving topical steroids per the recommended protocol defined anti-inflammatory regimen, consideration may be given to reducing the frequency of the topical steroids if the intraocular inflammation is controlled.

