1.0 INTRODUCTION

This statistical analysis plan provides details of the proposed statistical analyses for the clinical trial entitled “A Phase I/IIa Dose Escalation Safety Study of Subretinally Injected UshStat, Administered to Patients with Retinitis Pigmentosa Associated with Usher Syndrome Type 1B.” Study number TDU13600. This document contains a review of the study objectives and design, general statistical considerations, comprehensive statistical analysis methods for efficacy and safety endpoints, and a list of proposed tables and graphs. Any deviation from this statistical analysis plan will be described in the final study report, as appropriate.

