5.0 ENDPOINTS

5.1 Primary Endpoints

The primary objective of this study is evaluation of safety and tolerability of ascending doses of UshStat in patients with Usher syndrome type 1B. Safety and tolerability of the IMP will be evaluated using the following endpoints:

- The incidence of AEs over a 12-month period following a single intraocular dose of UshStat.
- Clinically important changes from baseline (Day -28) in the following safety assessments:
 - Best-corrected visual acuity (BCVA)
 - Slit-lamp examination
 - Indirect ophthalmoscopy
 - Fundus photography
 - Intraocular pressure (IOP)
 - Ocular coherence tomography (OCT)
 - Laboratory parameters
 - Vital signs
 - Concomitant medications
 - Physical examinations

For all primary endpoints with repeated measures, the primary time point will be considered the Week 48 (12-month) visit unless otherwise specified. BCVA and perimetry measurements are subject to broad intra-individual variability therefore the baseline value used for these measures will be an average of all the values obtained during the screening period.

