7.3.4 Intraocular Pressure (IOP)

The IOP for each visit will be measured using applanation tonometry. IOP will be listed by visit and eye. IOP for all patients' study eye and fellow eye will be presented graphically by visit and cohort. Mean changes in IOP by visit and cohort will be summarized in a table and graph by cohort and visit.

Clinically important changes and the number of individuals with $IOP \geq 25$, ≥ 30 , and ≥ 35 mmHg at any point from Day -28 to Week 48 will be tabulated by cohort and visit.

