8.3.2 BCVA, Ocular Inflammation and IOP

Table 3L lists the primary outcomes of BCVA, ocular inflammation and IOP for the study and fellow eyes by patient and visit, Tables 3M and 3N summarize mean changes in BCVA and IOP, respectively, by cohort and visit for the study and fellow eyes and Table 3O summarizes the number and percentage of individuals with elevated (≥ 25 , ≥ 30 and ≥ 35 mmHg) IOP in the study eye. Changes in ophthalmic inflammation by dose group, visit and eye will also be summarized in Table 3P. Ophthalmic outcome data will be displayed graphically in plots similar to Figures 3Q and 3R. Tables and plots will be given for the study eye as well as for the fellow eye, and labeled appropriately.

Table 3L: Ophthalmic Outcome Listing for Study Eye and Fellow Eye by Patient and Visit

Patient ID	Visit	Study	IOP		BCVA		Anterior Cells		Anterior Flare		Vitreous Cells		Vitreous Haze		Macular Edema	
			Fellow	Study	Study	Fellow	Study	Fellow	Study	Fellow	Study	Fellow	Study	Fellow	Study	Fellow

Table 3M: Mean Changes from Pre-surgical BCVA by Cohort and Visit

Cohort	Visit	Study Eye					Fellow Eye				
		N	Mean	Std	Min	Max	N	Mean	Std	Min	Max

Table 3N: Mean Changes from Pre-surgical IOP by Cohort and Visit

[figure not shown]
Cohort	Visit	Study Eye					Fellow Eye				
		N	Mean	Std	Min	Max	N	Mean	Std	Min	Max

Table 3O: Patients Experiencing Elevated IOP in the Study Eye Following Treatment by Cohort

Cohort	IOP ≥ 25 mmHg				IOP ≥ 30 mmHg				IOP ≥ 35 mmHg			
	No		Yes		No		Yes		No		Yes	
	N	%	N	%	N	%	N	%	N	%	N	%
1												
2												
3												
4												
5												
All												

[figure not shown]
Table 3P: Changes in Ophthalmic Inflammation in the Study Eye by Cohort and Visit

Cohort	Visit	Anterior Chamber Cells		Anterior Chamber Flare		Vitreous Cells				Vitreous Haze			
		No Change	Half-Step Increase	No Change	1-Step Increase	Half-Step Decrease	No Change	Half-Step Increase	2-Step Decrease	1-Step Decrease	No Change	Half-Step Increase	
		N	%	N	%	N	%	N	%	N	%	N	%

Figure 3Q: Ophthalmic Outcomes Over Time (Days from Surgery) by Patient

Mean changes from Baseline (Day -28) will be plotted for ophthalmic outcomes versus dose cohort in a plot similar to Figure 3R.

Figure 3R: Mean Change in Ophthalmic Outcome from Baseline by Dose Cohort

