The purpose of this memorandum is to document that the Table of Contents for the final analysis for TDU13600 will differ from the Table of Contents in the currently approved version 2 of the SAP, dated 22JUL2016. The format of the tables will be the same as those in the SAP, except that the adverse event tables will be updated to the format used for the 23MAY2018 DSMB Report for SAR422459. The TOC and the adverse event table shells to be used for the final TLFs are included below.

Coordinating Center

Statistician Signature:

[figure not shown]
Date: 30AUG2019

Sponsor Statistician

Signature:

[figure not shown]
Date: 04SEP2019

Coordinating Center

Director Signature:

Date: 24SEP2019

TOC FOR ALL TLFs FOR TDU13600

- [Table 1A](#): Screening and Surgery Dates and Visit Completion by Cohort
- [Figure 1B](#): Patient Flow Diagram
- [Table 1C](#): Study Follow-up Completion and Withdrawal (including deaths)
- [Table 2A](#): Demographics Summary by Cohort
- [Listing 2B](#): Detailed Demographic Listing by Cohort
- [Listing 2C](#): General Medical History by Patient
- Listing 2D: Study Eye Ocular History by Patient
- Listing 2E: Fellow Eye Ocular History by Patient
- [Table 2F](#): Baseline Physical Examination Parameters by Cohort
- Table 2G: Reproductive Status by Patient
- Listing 2H: Detailed Surgery Listing by Patient
- Table 3A: Number and Percentage of Patients Experiencing TEAEs or No Events by Type of Event and Cohort
- Table 3B: Number of Patients Experiencing TEAEs by MedDRA SOC, HLGT, HLT, PT, and Cohort
- Table 3C: Number of Patients with TEAEs of Special Interest by MedDRA SOC, HLGT, HLT, PT, and Cohort
- Table 3D: Number of Patients with SAEs by MedDRA SOC, HLGT, HLT, PT, and Cohort
- Table 3E: Number of Patients Experiencing Inflammatory TEAEs by MedDRA SOC, HLGT, HLT, PT, and Cohort
- Table 3F: Number of Patients with TEAEs Related to IMP by MedDRA SOC, HLGT, HLT, PT, and Cohort
- Table 3G: Number of Patients with TEAEs Related to Procedure by MedDRA SOC, HLGT, HLT, PT, and Cohort
- [Table 3H](#): Listing of Adverse Events Prior to Treatment by Patient and Cohort
- [Table 3I](#): Listing of TEAEs by Patient and Cohort
- [Table 3J](#): Listing of Treatment Emergent Adverse Events of Special Interest by Patient and Cohort
- Table 3K: Listing of Treatment Emergent Serious Adverse Events by Patient and Cohort
- [Listing 3L](#): Ophthalmic Outcome Listing for Study Eye and Fellow Eye by Patient and Visit

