- [Table 3M](#): Mean Changes from Pre-surgical BCVA by Cohort and Visit
- [Table 3N](#): Mean Changes from Pre-surgical IOP by Cohort and Visit

- Table 3O: Patients Experiencing BCVA Change in the Study Eye at Week 48 Following Treatment by Cohort
- Table 3P: Patients Experiencing Elevated IOP in the Study Eye at Week 48 Following Treatment by Cohort
- **Tables 3Q-3S:** Changes in Ophthalmic Inflammation in the Study Eye by Cohort and Visit
- Figures 3T-3V: BCVA in Study and Fellow Eyes by Patient in Cohort X
- Figures 3W-3Y: IOP in Study and Fellow Eyes by Patient in Cohort X
- Figure 3Z: Mean Changes in BCVA in the Study Eye over Time by Cohort
- Figure 3AA: Mean Changes in IOP in the Study Eye over Time by Cohort
- **Listing 3BB:** Listing of Patients with Abnormal and/or Clinically Significant Labs
- Listing CC: Abnormal Physical Examination Listing by Patient
- **Table 3DD:** Mean Change in Continuous Laboratory Parameters by Cohort and Visit
- **Listing 3EE:** OCT Listing by Patient and Visit
- Figures 3FF-3HH: Central Retinal Thickness (OCT) for Study and Fellow Eyes in Cohort X
- Figures 3II-3KK: Macular Volume (OCT) for Study and Fellow Eyes in Cohort X
- Table 3LL: Change from Baseline in Vital Signs by Cohort and Visit
- **Listing 4A:** Static (GATE) Perimetry Data by Patient
- Figures 4B-4D: Volume of Full Field Hill of Vision Measured by Static (GATE) Perimetry by Patient in Cohort X
- Figures 4E-4G: 111pt grid-Volume of Full Field Hill of Vision Measured by Static (GATE) Perimetry by Patient in Cohort X
- **Listing 4H:** Kinetic (SKP) Perimetry Data by Patient
- Figures 4I-4K: SKP Data in Study Eyes by Patient in Cohort X
- **Listing 4L:** Full Field ERG Response (Study Eye) Amplitude and Implicit Time Data by Cohort, Patient and Visit
- **Table 4M:** Mean Peak Amplitudes and Latencies at Baseline (mfERG) by Cohort and Patient
- **Table 4N:** Central Field (Rings 1-3) Summary mfERG Data by Cohort and Patient
- **Table 4O:** Peripheral Field (Rings 4-6) Summary mfERG Data by Cohort and Patient
- Listing 5A: Detailed Listing of Immunologic Results from Blood Samples by Cohort and Patient
- Listing 5B: Biodistribution Endpoint Data

ADVERSE EVENT TABLE SHELL FOR TDU13600

PRIMARY SYSTEM ORGAN CLASS HLGT: High Level Group Term HLT: High Level Term Preferred Term n(%)	Cohort 1 (1.4×10^5 TU) (N=3)	Cohort 2 (4.7×10^5 TU) (N=3)	Cohort 3 (1.4×10^6 TU) (N=3)	All Cohorts (N=9)
Any Class	X (X%)	X (X%)	X (X%)	X (X%)
SOC1	X (X%)	X (X%)	X (X%)	X (X%)

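### The final table list counts raised study-eye IOP at Week 48 only, whereas SAP 7.3.4 promises the count at any point, so rises that settled earlier drop out of the only IOP threshold table

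*SAP*

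**What the plan says.** IOP is one of the named primary safety assessments (Protocol 6.1, SAP 5.1). Four places in the SAP and its attached memorandum bear on how elevated values are counted.

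- **SAP 7.3.4** sets three thresholds (25, 30 and 35 mmHg, each inclusive). It says that the number of individuals reaching them "at any point from Day -28 to Week 48 will be tabulated by cohort and visit".
- **SAP 8.3.2, Table 3O (version 2 shell)** is titled "Patients Experiencing Elevated IOP in the Study Eye Following Treatment by Cohort". It has Yes and No columns for each threshold, one row per cohort and no visit limit.
- **The memorandum of 30 August 2019** lists the tables for the final analysis. Its Table 3P is "Patients Experiencing Elevated IOP in the Study Eye at Week 48 Following Treatment by Cohort". The memorandum states that the table of contents will differ from SAP version 2. It also says "The format of the tables will be the same as those in the SAP", with an exception only for the adverse event tables.
- **SAP 5.1** gives the default for primary endpoints with repeated measures: "the primary time point will be considered the Week 48 (12-month) visit unless otherwise specified".

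The memorandum gives no reason for the Week 48 limit and does not amend 7.3.4.

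**The concern.** A count at one visit and a count over the whole follow-up answer different questions. The second asks how many patients ever had a raised pressure in the treated eye after surgery. The first asks how many had one about a year later.

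Protocol 9.3.13 expects raised IOP as a post-surgical event. It provides for treatment and weekly review until the pressure stays below 25 mmHg, and it foresees rises while topical steroids are being given. Such rises may well have resolved long before Week 48, so the one visit retained is poorly placed to show them.

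If Table 3P is produced as titled, the only threshold summary in the final report could show no elevations in a cohort where some occurred. A reader who knows 7.3.4 and expects the any-point count could misread it.

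**Working it through.** The plan states no figure for this table, so there is none to reproduce. The check compares the texts and then counts visits.

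**1. The three descriptions side by side**

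| Source | Thresholds | Time span | Breakdown |
|---|---|---|---|
| SAP 7.3.4 | 25, 30, 35 mmHg | Any point, Day -28 to Week 48 | Cohort and visit |
| SAP 8.3.2, Table 3O (version 2) | 25, 30, 35 mmHg | After treatment, no visit limit | Cohort |
| Memorandum, Table 3P | Not in the title; format carried over from the SAP | Week 48 | Cohort |

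SAP 7.3.4 could mean one any-point count, a count at each visit, or both. A table for Week 48 alone satisfies none of these readings.

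**2. Does another final output supply the count?** The other IOP outputs in the memorandum's list are:

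- Table 3N and Figure 3AA: mean changes.
- Listing 3L: individual values by patient and visit.
- Figures 3W-3Y: individual plots.

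None counts patients by threshold.

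**3. Does the Week 48 default settle it?** The default in SAP 5.1 yields where something else is specified, and 7.3.4 specifies something else for these thresholds. SAP 7.0 names 48 weeks as the primary analysis time point, but it also says that results at all study visits will be presented.

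**4. Share of planned readings that Table 3P can use**

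Inputs: the IOP row of the schedule for Cohorts 1-3a (Protocol 2.1), with post-surgical visits at Day 1 and Weeks 1, 2, 4, 12, 24, 36 and 48; and N = 9 (three per cohort) from the adverse event shell in the memorandum.

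- Planned post-surgical study-eye readings: 8 × 9 = 72.
- Readings at Week 48: 1 × 9 = 9.
- Share used: 9/72 = 12.5%.
- Share that cannot enter: (72 - 9)/72 = 63/72 = 87.5%.

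This is a share of readings, not of elevations.

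**5. Possible effect on the patient count.** The documents do not say how many patients had a raised pressure. As an illustrative assumption, let 0 to 3 of the 9 patients reach 25 mmHg before Week 48 only, with no one at or above it at Week 48.

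- Any-visit count: 0/9 = 0% to 3/9 = 33%.
- Table 3P: 0/9 = 0% throughout, which follows from the assumption.
- Within a cohort of three, each such patient is 1/3 = 33%.

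**6. What the adverse event tables recover.** Protocol 9.3.13 states: "Raised IOP greater than 30 mmHg must be recorded as a post-surgical adverse event". Under that rule every reading of 35 mmHg or more reaches the adverse event tables, and so does every reading above 30 mmHg. Readings from 25 up to and including 30 mmHg fall under no such rule, although 25 and 30 are both SAP thresholds.

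**7. Two smaller gaps within the SAP.** The version 2 shell is by cohort only, so the by-visit count in 7.3.4 has no table in either list. The window in 7.3.4 opens at Day -28, before surgery, whereas the shell title covers the period after treatment.

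**The case against.** The strongest case for leaving the table alone has five parts.

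- **The limit is disclosed and looks deliberate.** The title says Week 48, a matching BCVA table at Week 48 appears beside it, and the memorandum has signature lines for both statisticians and the coordinating center director. This stands and makes misreading less likely. It does not supply a reason, and a deliberate change needs one more than a slip would.
- **Week 48 has broad support in the plan.** Protocol 13.4.2 and SAP 5.1, 7.0 and 7.3 all point to it. That justifies having a Week 48 table. It does not justify dropping the count that the specific IOP section promises.
- **The memorandum keeps only the format unchanged, and a time point is content.** That is a fair reading, so the sentence on format is weak evidence of a contradiction. The conflict with 7.3.4 does not depend on it.
- **Little is lost in practice.** With nine patients the any-visit count can be rebuilt from Listing 3L, rises above 30 mmHg are adverse events, and SAP 8.0 keeps the version 2 table among the minimum content of DSMB reports. All of this stands and limits the severity. A reader should still not have to reconstruct a pre-specified safety summary from a listing.
- **The sizes are not evidence of missed elevations.** Correct. The 87.5% describes readings, and the upper end of 0 to 3 patients is arbitrary.

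It is also true that no breach of the rule on reporting deviations can be shown, because the final study report is not among the documents.

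**Conclusion.** The concern holds and should be fixed. As written, the final table list does not deliver the threshold count that SAP 7.3.4 specifies, and nothing else in the list replaces it. Any patient at or above a threshold between Day 1 and Week 36, but below it at Week 48, is counted as No. A patient with no Week 48 reading cannot be classified at all, since SAP 6.3 rules out replacing missing values.

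For the nine patients in the memorandum's shell, 63 of 72 planned readings cannot contribute. This assumes the visit schedule for Cohorts 1-3a and complete attendance. How many patients would change category is unknown from the documents.

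The damage is confined to the summary. Individual readings stay in the report, and the main uncovered range is 25 to 30 mmHg where no adverse event was reported.

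**What to change.** 1. Restore the table of patients with study-eye IOP of at least 25, 30 and 35 mmHg at any post-surgical visit, Day 1 to Week 48, by cohort.
2. Add the by-visit count that 7.3.4 promises, and keep Week 48 as a separate column.
3. State that the any-point window starts after surgery, so that 7.3.4 and the shell title agree.
4. If the Week 48 restriction is intended, record it with its reason as a departure from 7.3.4. SAP 1.0 already provides for this: "Any deviation from this statistical analysis plan will be described in the final study report".

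The cost is one table shell and one line in the memorandum. All the data are already collected.

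### The final table list limits the elevated-IOP count to Week 48 although SAP 7.3.4 counts elevations at any point, so early rises that settle show as zero in the only IOP threshold table

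*SAP*

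**What the plan says.** IOP is one of the listed primary safety assessments (Protocol 6.1, SAP 5.1). Four places bear on how elevations are summarised.

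- **SAP 7.3.4** sets the counting rule. The number of individuals at or above 25, 30 and 35 mmHg "at any point from Day -28 to Week 48 will be tabulated by cohort and visit".
- **SAP 8.3.2** gives the shell, Table 3O: "Patients Experiencing Elevated IOP in the Study Eye Following Treatment by Cohort". It has yes/no columns for the three thresholds and one row per cohort. It names no visit.
- **The memo of 30 August 2019**, appended to the SAP, replaces the table of contents for the final analysis. It lists the table as 3P: "Patients Experiencing Elevated IOP in the Study Eye at Week 48 Following Treatment by Cohort". It prints no shell for 3P and does not amend 7.3.4. On layout it says: "The format of the tables will be the same as those in the SAP, except that the adverse event tables will be updated".
- **SAP 5.1** sets the default for primary endpoints with repeated measures: "the primary time point will be considered the Week 48 (12-month) visit unless otherwise specified".

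On adverse events, Protocol 9.3.13 states: "Raised IOP greater than 30 mmHg must be recorded as a post-surgical adverse event". It then describes pressure-lowering drops and weekly review until IOP stays below 25 mmHg.

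**The concern.** The memo's title adds a visit limit that neither SAP 7.3.4 nor the SAP shell contains, and nothing in the memo explains it. The two rules answer different questions. The SAP rule asks how many patients ever had raised pressure during the year. The memo's title asks how many still have it at the last visit.

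For a surgical procedure followed by steroids, the first question is the one that describes tolerability. Protocol 9.3.13 itself treats raised IOP as a post-surgical complication, including during topical steroid use, and directs that it be managed until it resolves. A patient managed that way would normally be below every threshold by Week 48. At stake is how the study report reads: a row of zeros in Table 3P could be taken to mean that no eye had raised pressure, when it says only that none did at one visit.

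**Working it through.** No figure in the plan needs reproducing. The check compares definitions and counts scheduled visits.

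**1. The three definitions side by side**

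| Source | Window | Eye | Breakdown |
|---|---|---|---|
| SAP 7.3.4 | any point, Day -28 to Week 48 | not restricted | cohort and visit |
| SAP 8.3.2, Table 3O shell | after treatment, no visit named | study eye | cohort |
| Memo, Table 3P (title only) | Week 48 | study eye | cohort |

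The first two differ in detail, but neither is limited to one visit.

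**2. Other IOP outputs in the memo**

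- Listing 3L: values by patient, visit and eye (IOP is in the SAP shell).
- Figures 3W-3Y: patient plots.
- Table 3N, "Mean Changes from Pre-surgical IOP by Cohort and Visit": the SAP shell gives N, mean, SD, minimum and maximum change.
- Figure 3AA: mean changes over time.

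None counts patients at or above a threshold, so Table 3P is the only one that does.

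**3. Readings used**

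- Post-operative IOP visits for Cohorts 1-3a (Protocol 2.1): Day 1 and Weeks 1, 2, 4, 12, 24, 36 and 48, so 8.
- Patients in the memo's adverse event shell: 3 + 3 + 3 = 9.
- Scheduled post-operative study-eye readings: 9 × 8 = 72.
- Used by Table 3P: 9 × 1 = 9.
- Left out: 72 − 9 = 63, and 63/72 = 87.5%.

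The full 7.3.4 window adds the two pre-surgical visits: 9 × 10 = 90 study-eye readings, of which Table 3P uses 9 (10%).

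**4. Timing under the current protocol**

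The topical steroid taper in Protocol 9.2.2 has four steps of 7-10 days, so 4 × 7 = 28 to 4 × 10 = 40 days. Week 48 is day 48 × 7 = 336, which is 296 to 308 days after the taper ends. Some or all of the nine patients may have been treated under earlier amendments, so this shows the intended course and is not a record of what they received.

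**5. What adverse event reporting covers**

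The numeric trigger in Protocol 9.3.13 is above 30 mmHg. Readings from 25 up to and including 30 mmHg reach at least the lowest SAP threshold without meeting it. The general definition in Protocol 11.1 may still capture some of them.

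**6. Illustration, on assumed rates**

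The documents give no IOP results. Let p be the chance that a patient reaches 25 mmHg only before Week 48, independently across patients. The expected number missed is 9p, and the chance of missing at least one is 1 − (1 − p)^9.

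| Assumed p | Expected missed of 9 | Chance of at least one |
|---|---|---|
| 10% | 0.9 | 61% |
| 20% | 1.8 | 87% |
| 30% | 2.7 | 96% |

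If one, two or three such eyes occurred and no eye was raised at Week 48, Table 3P would show 0/9 where an any-visit count shows 1/9 (11%), 2/9 (22%) or 3/9 (33%).

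**The case against.** The strongest defence is that Week 48 is the plan's own time point. SAP 7.0 makes it the primary analysis time, SAP 7.3 compares Day -28 with Week 48 for these endpoints, and the memo gives BCVA a parallel Week 48 table. This does not settle the matter. SAP 5.1 makes Week 48 a default that yields where something else is specified, and 7.3.4 specifies something else for this count. SAP 7.0 also promises results at all visits.

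A second defence is that the limit rests on a title. No 3P shell is printed, and the title might be meant as 'by Week 48'. That cannot be excluded, but it is not the plain meaning. If it is what was meant, the title needs correcting. For the same reason the memo's statement about unchanged format is weak evidence either way, since format may mean layout only.

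A third defence largely stands. A reader might infer that early rises vanish from the report, and the documents do not support that. Listing 3L and Figures 3W-3Y show every value, and for nine study eyes the count can be made by hand. Table 3N's maximum would reveal a spike at a given visit. With three patients in a cohort, the mean, minimum and maximum even fix all three changes, up to rounding. What Table 3N lacks is the level reached, because it reports change from the pre-surgical value. It also cannot link a patient across visits.

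Two further limits stand. Protocol 13.4.2 requires no threshold count, so the shortfall is against the SAP and not the protocol. And 7.3.4 and the Table 3O shell already differ from each other, so a corrected table has to say which it follows.

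**Conclusion.** The conflict is real. The memo narrows the only IOP threshold table from any point to a single visit, against SAP 7.3.4 and without a stated reason. As titled, the table uses 1 of 8 scheduled post-operative visits and leaves out 87.5% of the scheduled study-eye readings after surgery. A 0/9 in it is compatible with anything from 0/9 to 9/9 patients having had raised pressure earlier. The consequence is greatest from 25 to 30 mmHg, where no numeric adverse event trigger applies.

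The defect is a misleading summary count and not lost data. It would be wrong to conclude that any particular number of rises has been missed: the documents report no IOP results, and the scenarios above are assumptions. The conclusion rests on reading the title literally, on the Protocol 2.1 schedule for Cohorts 1-3a, and on the nine patients in the memo's adverse event shell. In a descriptive study this does not threaten the analysis, but it concerns a primary safety assessment and should be corrected.

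**What to change.** - Make Table 3P the number and percentage of patients with study-eye IOP at or above 25, 30 and 35 mmHg at any visit after surgery through Week 48, by cohort. This follows the SAP Table 3O shell.
- Add the by-visit counts that SAP 7.3.4 calls for, with the pre-surgical visits shown separately and Week 48 as one of the visits.
- If the Week 48 limit is kept, state it and the reason as a deviation from SAP 7.3.4. SAP 1.0 already provides for this: "Any deviation from this statistical analysis plan will be described in the final study report, as appropriate".

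The cost is one table re-run on data already collected, or one sentence in the report. No new data are needed.

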7.3 Primary Endpoint

The primary endpoint is composed of several endpoints related to safety, each of which will be presented at the patient and eye level (refer to [Sections 8](#) and [9](#)). Primary analysis for these endpoints, except adverse events, will compare change from Day -28 to Week 48. Graphical presentation of cohort summaries will also be presented as described, and clinically important changes from Baseline (Day -28) to Week 48 will be indicated and summarized.

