7.3.3 Ocular Inflammation

The grading system of ocular inflammation can be found in Appendix A of the study protocol. The inflammatory grades will be treated as ordinal variables and plotted by patient over time. Scores for ocular inflammation, including anterior chamber cells, flare (slit lamp examination) and vitreous cells, haze (indirect ophthalmoscopy) and macular edema, will be listed by eye and shown graphically similar to the other ophthalmic endpoints. Summary counts for the number of 'step-up' and 'step-down' changes in the inflammation scale in the study eye may be tabulated by cohort and visit. Clinically important changes (i.e., ≥ 2 step change) as observed in slit lamp examination and/or indirect ophthalmoscopy at any point from Day -28 to Week 48 will be indicated and listed where appropriate.

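### The final table list summarises study-eye inflammation grades only visit by visit: it has no count of patients who ever had a clinically important rise, and it lacks the by-patient plots promised in SAP 7.3.3

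*SAP*

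**What the plan says.** SAP 5.1 makes "Clinically important changes from baseline (Day -28) in the following safety assessments" part of the primary endpoint; slit-lamp examination and indirect ophthalmoscopy are on the list that follows. SAP 7.3 sets the primary comparison, adverse events apart, as change from Day -28 to Week 48, and adds that "clinically important changes from Baseline (Day -28) to Week 48 will be indicated and summarized".

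SAP 7.3.3 deals with inflammation. "The inflammatory grades will be treated as ordinal variables and plotted by patient over time". Counts of steps up and down by cohort and visit are optional. A change of two or more steps is clinically important, and such changes "at any point from Day -28 to Week 48 will be indicated and listed where appropriate".

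The 2019 memorandum replaces the table of contents for the final analysis and keeps the SAP table formats, except for adverse events. Its only grade-based inflammation summary is Tables 3Q-3S, "Changes in Ophthalmic Inflammation in the Study Eye by Cohort and Visit". By-patient figures exist for acuity (Figures 3T-3V, "BCVA in Study and Fellow Eyes by Patient in Cohort X"), pressure, OCT thickness and volume, and perimetry. Listing 3L gives ophthalmic outcomes by patient and visit.

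**The concern.** Inflammation is the main expected hazard. Protocol 4.5 reads the monkey toxicology as consistent with a transient, dose-related inflammatory response. The rationale for Amendment 8 reports a serious uveitis case in this study. Protocol 8.5 makes severe or persistent ocular inflammation a dose-limiting toxicity.

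A transient response will usually be over by Week 48, so the Week 48 row says little about it. A reader of the report will want two numbers per dose: how many treated eyes ever had a clinically important rise, and how high it went. Visit-by-visit counts do not in general give the first number. The plots that would show each eye's course are not on the list.

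**Working it through.** The plan states no figure on this point, so there is none to reproduce. The check is of outputs, followed by a small illustration.

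**1. Outputs.** Reading every line of the memorandum's list against SAP 7.3, 7.3.3 and 8.3.2:

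| Item | Outputs in the final list |
|---|---|
| Grade summary by cohort and visit | Tables 3Q-3S |
| Any-time patient count of changes of two or more steps | none |
| Worst grade or maximum increase per patient | none |
| By-patient inflammation figures | none |
| Grades by patient and visit | Listing 3L |

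The missing figures depart from SAP 7.3.3. The missing count does not break a specific promise.

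**2. Adverse event tables.** Memorandum Table 3E counts patients with inflammatory treatment-emergent events, without severity. Its term list in SAP 7.3.1 includes vitreous floaters, eye discharge and subretinal fluid, so it does not measure grade change. Protocol 9.3.13 requires inflammation to be recorded as a post-surgical event only if it worsens during the steroid regimen, or persists or appears after it. The ocular special-interest cut in Protocol 11.5 is more than two steps, so a rise of exactly two can fall outside Table 3C.

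**3. What by-visit counts determine.** Let c1 to c4 be the numbers of patients with a rise of two or more steps at Day 1 and Weeks 1, 2 and 4, in a group of N. Without restriction on pattern, the number ever affected lies between max(c) and min(N, sum of c). The counts below are assumed, not trial data.
- N = 3, counts 1, 1, 1, 0: from 1 to min(3, 3) = 3. Of 3 × 3 × 3 = 27 arrangements, 3 give one patient, 18 give two and 6 give three.
- N = 3, counts 2, 1, 0, 0: from 2 to min(3, 3) = 3. Of 3 × 3 = 9 arrangements, 6 give two patients and 3 give three.
- N = 2, counts 1, 1, 0, 0: from 1 to min(2, 2) = 2.
- N = 1: never ambiguous.

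For N = 3 there are 4^4 = 256 possible count sets. The number is undetermined when max(c) is below 3 and the sum exceeds max(c). That gives 11 sets with maximum 1 (16 − 5) and 61 with maximum 2 (81 − 16 − 4), so 72 in all. If each eye has one unbroken episode, 39 of 156 attainable sets are ambiguous. If every episode also starts at Day 1, 0 of 35 are. The sets are not equally likely, so none of these is a probability.

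**4. Step rule.** The printed shell for inflammation changes (SAP 8.3.2, Table 3P) labels an anterior chamber cell column as a half-step increase. That implies steps by grade number. A two-step rise from grade 0 then begins at 2+, which is 16-25 cells per field in Protocol Appendix A.

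**5. Dose within Cohort 3.** The memorandum's adverse event shell heads Cohort 3 as 1.4×10^6 TU, N = 3. By measured strength (Protocol synopsis and Table 3), one eye received 0.33×10^6 TU and two received 2.4×10^6 TU. The ratio is 2.4 / 0.33 = 7.3, and no eye among these three received 1.4×10^6 TU.

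**The case against.** The strongest reply is that nothing is lost. With nine patients and Listing 3L, anyone can count affected eyes exactly. The largest rise in a cohort can be read from the highest step column filled at any visit. Tables 3C to 3E already count patients with inflammatory, special-interest and serious events. If inflammation starts at Day 1 in every affected eye, which is plausible after vitrectomy and subretinal injection, the Day 1 row gives the exact count. All of this stands, and it limits the weight of the point. It does not supply the plots, and it leaves the reader to compile a primary safety result by hand.

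Three stronger readings are tempting.
- A reader might infer that the memorandum withdrew a promised any-time count. It did not: SAP 7.3.3 says such changes will be indicated and listed. The wording about summarising is general, in SAP 7.3, and can be read as the Week 48 change only. SAP 7.3.4 did plan pressure counts "at any point from Day -28 to Week 48 will be tabulated by cohort and visit", with the shell "Patients Experiencing Elevated IOP in the Study Eye Following Treatment by Cohort", but the memorandum retitles that table to Week 48, so the precedent is weak.
- A reader might infer that half steps are undefined. The shell label settles this well enough. Appendix A gives no vitreous-cell scale, but that is missing detail and may sit in site documents.
- A reader might infer that no by-patient inflammation display will exist anywhere. The patient profiles in SAP 9 are not withdrawn, and some of their figures are not visible in the available copy, so this cannot be said. The point concerns the memorandum's list.

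**Conclusion.** The point holds as a cheap improvement of modest weight. The final list omits the by-patient inflammation plots that SAP 7.3.3 says will be made. It also gives no any-time count for a change that the same section calls clinically important at any point. This is a gap in the summary and not in the data.

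Its practical size depends on when rises begin. There is no ambiguity if every affected eye is raised at Day 1 and settles without recurrence. With staggered onset in a cohort of three, the number ever affected can range from one to three. The conclusion assumes that Tables 3Q-3S keep the SAP's cohort-by-visit layout, as the memorandum says, and that the final set is the nine patients in its shell.

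**What to change.** Keep the by-visit rows, which are needed because the stopping criterion in Protocol 8.4 concerns inflammation not resolving by 28 days. Then:
- Add to Tables 3Q-3S one any-time block for the study eye, using all examinations from Day 1 to Week 48. For each recorded scale give the maximum increase from baseline, the worst grade, and n/N patients with an increase of two or more steps, counted by grade number.
- Show Cohort 3 by measured dose (n = 1 at 0.33×10^6 TU, n = 2 at 2.4×10^6 TU), not as a single 1.4×10^6 TU group.
- Restore the by-patient inflammation figures in the format of Figures 3T-3V.
- Footnote that a worst-ever grade includes expected early post-surgical inflammation and should be read beside the by-visit rows.

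The cost is a little programming on grades already in Listing 3L for nine patients, plus a line or two in the memorandum. No new data are needed. The downside is that a worst-ever grade mixes surgical inflammation with any vector effect, which is why the footnote is needed.
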